### Evidence from clinical evaluation/investigations

- Software enables to provide recommendations and suggestions for knowledge related to diagnosis, prognosis and/or treatment: scientific literature confirms that SW system functions and features are aligned with current user requirements as described in relevant publications and as included in the DUE.

Dilemma Solutions S.L.	CHAPTER 06-1C	TD01-06-1C Ver.: 01 2025/03/03
	CLINICAL EVALUATION PLAN (CEP)	Page 13 of 38

- Increase of appropriate recommendations: number of appropriate recommendations – an observational, single-centre study consisting on a clinical validation of a CDSS applied to retrospective clinical cases of cardiology patients with valvular heart disease, shall confirm an increase in the number of appropriate recommendations by by a factor of three over the recommendations generated with general management without the support system.
- Inappropriate recommendations: number of inappropriate recommendations – an observational, single-centre study consisting on a clinical validation of a CDSS applied to retrospective clinical cases of cardiology patients with valvular heart disease, shall confirm that naevia medical, compared to conventional management, is able to reduce the number of inappropriate and mising recommendations based on scientific evidence in the diagnostic and therapeutic areas.
- Concordance between expert evaluators:
  - o The analysis of the degree of agreement/disagreement in the different domains, evaluated using a Likert scale, analysed using ordinal regression (Joshi, Kale et al. 2015). Response options: 1. Strongly disagree, 2. Disagree, 3. Neither agree nor disagree, 4. Agree, 5. Strongly agree.
  - o The panel's agreement with the CDSS was very high, with a mean Likert scale score above 4 in all domains (STD: 4.53, LTD: 4.68, CMT: 4.58, ITI: 4.62). The probability of strongly agreeing was significantly higher than the probability any of the other categories (z.ratio (5|1)= 30.88, p-value< 0.001, z.ratio (5|2)= 31.67, p-value < 0.001, z.ratio (5|3) = 30.21, p-value< 0.001, z.ratio (5|4)= 22.54, p-value< 0.001).

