### **11. Basis to determine the acceptability of the benefit-risk ratio**

Dilemma Solutions S.L.	CHAPTER 06-1C	TD01-06-1C Ver.: 01 2025/03/03
	CLINICAL EVALUATION PLAN (CEP)	Page 23 of 38

Naevia Medical is a clinical decision support software (CDSS) that, based on clinical input data (history, symptoms, complementary test data...) of adult patients with heart disease, provides healthcare professionals with prioritized, justified and referenced recommendations and knowledge suggestions related to diagnosis and/or treatment (recommended tests, medications,...).

The main clinical benefit obtained with the DUE is the following:

- Direct clinical benefit to provide healthcare professionals with recommendations and suggestions for knowledge related to diagnosis, prognosis and/or treatment.

The main complications associated with the use of product category are the following:

- Misdiagnosis caused by product's error.
- Misdiagnosis caused by user's errors.
- Patient's privacy and data security.

The risk-benefit ratio is favorably justified when the benefits in improved quality of care, increased appropriate recommendations and decreased inappropriate recommendations outweigh the risks associated with the use of CDSS. This requires careful knowledge modelling, correct implementation, constant monitoring and continuous updating. Acceptance of the system by clinical users is crucial and must be ensured through appropriate training, support and participation in system improvement.

Clinical benefits and possible complications or side effects related to the use of naevia Medical will be further investigated and assessed in the planned literature searches and included in the Clinical Evaluation Report (see Benefit-Risk Analysis in section 5 of the Technical Documentation).

Based on the state of the art in medicine, the acceptability of the DUE benefit-risk ratio for the indications mentioned above, depends on clinical safety and performance parameters and outcomes as listed below.

Dilemma Solutions S.L.	CHAPTER 06-1C	TD01-06-1C Ver.: 01 2025/03/03
	CLINICAL EVALUATION PLAN (CEP)	Page 24 of 38

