**Table 1 – Naevia Medical – Indicative List of Clinical Safety and Performance Parameters and Quantitative Measures**

Parameter / Outcome	Quantitative Measure of Performance	Source / Level of Evidence Required	
Performance of Naevia medical to provide healthcare professionals with recommendations and suggestions for knowledge related to diagnosis, prognosis and/or treatment			
Software enables to provide recommendations and suggestions for knowledge related to diagnosis, prognosis and/or treatment	
Goal: all basic key characteristics of CDSS are supported and all supported characteristics work correctly and as expected.
 
[references to sources]
 
*EN ISO 62304 – Medical device software – Software life-cycle processes
 
EN 82304 – Health Software – Part 1: General requirements for product Safety
	Preclinical	
Accepted if using the system functions and features, users are able to get recommendations and suggestions for knowledge related to diagnosis, prognosis and/or treatment.
 
 
- V&V per EN ISO 62304 and install validation. All tests provide recommendations and suggestions and thus CDSS is verified by all tests.
 
- V&V per EN 82304 and install validation. All tests provide recommendations and suggestions and thus CDSS is verified by all tests.
 
- Usability testing of the software by representative users to successfully provides recommendations and suggestions for knowledge related to diagnosis, prognosis and/or treatment.
 

		Clinical	
Accepted if system features cover user needs for getting recommendations and suggestions for knowledge related to diagnosis, prognosis and/or treatment aligned with the tools required for medical diagnosis support and using the system functions and features, users successfully use CDSS to make clinical decisions regarding diagnosis, prognosis and/or treatment.
 
 
- V&V per EN ISO 62304 and install validation. All tests provide recommendations and suggestions and thus CDSS is verified by all tests*.
 
- V&V per EN 82304 and install validation. All tests provide recommendations and suggestions and thus CDSS is verified by all tests.
 

Dilemma Solutions S.L.	CHAPTER 06-1C	TD01-06-1C Ver.: 01 2025/03/03
	CLINICAL EVALUATION PLAN (CEP)	Page 25 of 38

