	43(7), https://doi.org/10.1093/eurheartj/ehab395	561-632.		
Appropriate recommendations	Increase the number of appropriate recommendations by a factor of three	Clinical	-	An observational study consisting on a clinical validation of a CDSS applied to retrospective clinical cases of cardiac patients with valvular heart disease, shall confirm an increase in the number of appropriate recommendations by a factor of three over the recommendations generated with conventional management without the support system.
Inappropriate recommendations	Reduction of inappropriate recommendations	Clinical	-	An observational study consisting on a clinical validation of a CDSS applied to retrospective clinical cases of cardiac patients with valvular heart disease, shall confirm that Naevia medical, compared to conventional management, is able to significantly decreased the number of inappropriate and missing recommendations in all the domains analyzed.

Dilemma Solutions S.L.	CHAPTER 06-1C	TD01-06-1C Ver.: 01 2025/03/03
	CLINICAL EVALUATION PLAN (CEP)	Page 27 of 38

Concordance between expert evaluators	Professionals agreement [reference to sources]  *Joshi, A., S. Kale, S. Chandel and D. K. Pal (2015). "Likert Scale: Explored and Explained." Current Journal of Applied Science and Technology 7: 396-403.	Clinical	
 
- The panel's agreement with the CDSS was very high, with a mean Likert scale score above 4 in all domains (STD: 4.53, LTD: 4.68, CMT: 4.58, ITI: 4.62). The probability of strongly agreeing was significantly higher than the probability any of the other categories (z.ratio (5 1)= 30.88, p-value< 0.001, z.ratio (5 2)= 31.67, p-value < 0.001, z.ratio (5 3) = 30.21, p-value< 0.001, z.ratio (5 4)= 22.54, p-value< 0.001).
 
-
 

Safety of Naevia medical			

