### Main clinical investigation

Title	Clinical validation study of naevia medical, a decision support tool for valvular heart disease
Registration number	ClinicalTrials.gov ID NCT06392464
Start and End	2024
Publication	Pending
Design	pre-test-post-test of a randomly assigned group, using a longitudinal repeated measures approach and retrospective validation
Duration	3 months
Centres	Instituto de Investigación Sanitaria de Santiago de Compostela (IDIS)
Sponsor	DILEMMA SOLUTIONS SL
Main objective	Demonstrate that the use of the naevia medical CDSS significantly increases appropriate recommendations based on clinical practice guidelines, and decreases the number of inappropriate recommendations received by the patient, compared to conventional management.
Device investigation under	Naevia medical
Number of participants	101

Dilemma Solutions S.L.	CHAPTER 06-1C CLINICAL EVALUATION PLAN (CEP)	TD01-06-1C Ver.: 01 2025/03/03
		Page 33 of 38

Title	Clinical validation study of naevia medical, a decision support tool for valvular heart disease	
Inclusion criteria	
Retrospective clinical retrospective cases of patients with valvular heart disease will be selected in a stratified randomised manner from among:
 
 
(i) patients presented at a medical-surgical session.
 
ii) patients from the monographic consultation of valvopathies.
 
 
Inclusion criteria:
 
 
- Clinical cases of patients randomly selected from among those presented during the year 2022 in medical-surgical session with the main diagnosis of aortic valvular stenosis, aortic insufficiency, mitral stenosis and mitral insufficiency (greater than moderate grade). Randomisation will be stratified ensuring that 50% come from the medical-surgical session.
 
- Clinical cases of patients randomly selected from clinical records of the Valvopathy Consultation seen in 2022 with the main diagnosis of aortic stenosis, aortic insufficiency, mitral stenosis and mitral insufficiency (major degree).
 
mitral regurgitation (greater than moderate grade). Randomisation will be stratified by ensuring that at least 40% of patients have aortic valve disease and 20% have mitral valve disease.
 
- Age <math>\geq 18</math> years.
 
	

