Exclusion criteria	
 
- Subjects under 18 years of age.
 
- Inability to anonymise the case.
 
- Clinical cases of valvular heart disease involving complex congenital heart disease.
 
- Clinical cases that do not meet the minimum set of data necessary for decision-making.
 
- Clinical cases with a principal diagnosis other than valvular heart disease.
 
- Presence of bacterial endocarditis.
 
	
Primary and Secondary Outcomes	
It is considered clinically beneficial to increase the number of appropriate recommendations by 15% over the recommendations generated with general management without the support system.
 
The baseline/pre-test value is the number of appropriate recommendations based on clinical practice guidelines during conventional management (without CDSS). Inappropriate recommendations as judged by the committee of expert assessors during conventional management will also be collected.
 
The post-intervention/post-test value is the number of appropriate guideline-based recommendations after activation of the naevia medical decision support system. Inappropriate recommendations in the judgement of the committee of assessors during CDSS management will be collected.
 
To calculate the percentage increase between two values we will use the following formula:
 $\text{Percentage increase} = (\text{Post-intervention value} - \text{Baseline value}) / \text{Baseline value} \times 100$	

Dilemma Solutions S.L.	CHAPTER 06-1C	TD01-06-1C Ver.: 01 2025/03/03
	CLINICAL EVALUATION PLAN (CEP)	Page 34 of 38

Title	Clinical validation study of naevia medical, a decision support tool for valvular heart disease
	value) ×100%.
Protocol reference	TD01-06-1C-06-02 CIP_NCT06392464

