### **Analysis of the amount and quality of recommendations**

The impact of the CDSS activation on the recommendations will be assessed by analyzing the *number* of recommendations (appropriate, inappropriate, missing) per patient. The mean number of appropriate, inappropriate, and missing relevant recommendations generated per patient will be compared before and after the CDSS activation. Descriptive statistics, including mean (standard deviation [SD]), median (interquartile range [IQR]), and range, will be reported for these counts. To statistically compare the distributions of the *number* of appropriate, inappropriate, and missing recommendations per patient before and after CDSS implementation, the Wilcoxon signed-rank test will be applied.

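### Two figures for the increase in appropriate recommendations (15% and a factor of three) are given no stated relation, and the SAP's test against zero cannot confirm either

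*Protocol*

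**What the plan says.** **The 15% figure.** Protocol section 14, Main clinical investigation, row Primary and Secondary Outcomes: "It is considered clinically beneficial to increase the number of appropriate recommendations by 15% over the recommendations generated with general management". The same row defines the percentage increase as (post − baseline) / baseline × 100. It does not say whether the values are totals, means or per-patient counts.

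**The threefold figure.** Section 7.1 says that an observational, single-centre validation on retrospective valvular cases "shall confirm an increase in the number of appropriate recommendations by by a factor of three" over management without the system. Table 1 in section 11 repeats it as the performance measure for appropriate recommendations: the study "shall confirm an increase in the number of appropriate recommendations by a factor of three".

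**The link to benefit-risk.** Section 11 says that acceptability of the benefit-risk ratio "depends on clinical safety and performance parameters and outcomes as listed below". The list is Table 1, which is headed "Indicative List of Clinical Safety and Performance Parameters and Quantitative Measures".

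**The objective and the analysis.** The main objective in section 14 is to demonstrate that use of the system "significantly increases appropriate recommendations based on clinical practice guidelines"; no size is attached. The SAP (Analysis of the amount and quality of recommendations) compares mean counts per patient before and after activation. It says that mean (SD), "median (interquartile range [IQR]), and range, will be reported for these counts", and applies a Wilcoxon signed-rank test. It mentions neither 15%, nor threefold, nor the percentage increase, nor a confidence interval.

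**The concern.** The two figures are far apart, and nothing in the supplied documents says how they relate or which one decides whether the Table 1 criterion for appropriate recommendations is met. A result between them could be reported as a success by the outcomes row and as a failure by Table 1.

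The SAP does not settle this. Table 1 asks the study to confirm a stated size of increase, whereas the only planned inference is whether there is any shift at all. The observed increase can be worked out from the reported means and set against either figure. Without an interval, however, the reader cannot tell how firmly an increase near a threshold supports a claim to have reached it.

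**Working it through.** **1. Is it one study?** Sections 7.1 and 11 give no registration number, so this is an inference. Section 7.1 describes an observational, single-centre clinical validation on retrospective valvular cases. Section 14 lists one clinical validation study in valvular disease, with one centre and retrospective cases. Its other entries are a colorectal screening study, a hypertrophic cardiomyopathy study, registries, and work in other conditions. The inference is strong.

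**2. Put both figures on the protocol's scale**, (post − baseline) / baseline × 100:
- 15% is a post/baseline ratio of 1.15.
- Threefold, read as post = 3 × baseline: (3 − 1) × 100 = +200%, ratio 3.0.
- Threefold, read as an increase of 3 × baseline: (4 − 1) × 100 = +300%, ratio 4.0.
- Relative size: 200/15 = 13.3 times the first figure, or 300/15 = 20 times.

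Any observed increase from 15% to just under 200% (just under 300% on the other reading) meets one figure and misses the other.

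**3. What can the planned test show?** The signed-rank test has a null of no shift. An extreme illustration, with assumed baseline means because the documents give none: of 101 cases, 6 gain one recommendation each and 95 are unchanged.
- Exact two-sided p = 2 × 0.5⁶ = 0.031.
- Increase in the mean: at a baseline mean of 3, 6/303 = 2.0%; at 5, 6/505 = 1.2%; at 8, 6/808 = 0.7%; at 12, 6/1212 = 0.5%.

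The test is significant with an increase far below 15%. This shows only that significance is not size; it does not predict this study's data.

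**4. How wide might the missing interval be?** The documents give no SD or baseline mean, so the ratio r = (SD of paired difference) / (baseline mean) is assumed. With a normal approximation and the baseline mean treated as fixed, the half-width in percentage points is 1.96 × r / √101 × 100.

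| r (assumed) | Half-width | Observed increase for lower limit above 15% | Observed increase for lower limit above 200% |
|---|---|---|---|
| 0.25 | 4.9 | 19.9% | 204.9% |
| 0.5 | 9.8 | 24.8% | 209.8% |
| 1.0 | 19.5 | 34.5% | 219.5% |
| 1.5 | 29.3 | 44.3% | 229.3% |
| 2.0 | 39.0 | 54.0% | 239.0% |

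Under this approximation, the half-width is also the observed increase that would just reach two-sided p = 0.05 against zero. At the larger values of r that increase is itself above 15%, but the lower limit still lies at zero, so the 15% figure is not established by significance alone.

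**The case against.** The strongest reply is that there is no conflict. Fifteen per cent is described as beneficial; threefold is what the study must confirm. Meeting threefold also meets 15%. Section 11 ties benefit-risk to Table 1, whose only figure for appropriate recommendations is threefold. This stands as the most natural reading, and a reader who inferred that the protocol contradicts itself would go too far. What remains is that no supplied sentence says it, and that Table 1 is headed as indicative.

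Three other stronger readings are not supported:
- **That the benefit-risk conclusion turns on this one number.** Section 11 states a qualitative weighing of benefits against risks, and Table 1 lists several other performance and safety parameters.
- **That a threshold was chosen after the results were seen.** The study is dated 2024 and the plan 2025/03/03, and the plan already reports that the panel's "agreement with the CDSS was very high, with a mean Likert scale score above 4 in all domains". Those are agreement scores. No counts of appropriate recommendations are reported, and neither threshold is dated.
- **That the SAP cannot address the increase at all.** It compares means, so a point estimate can be derived, and the Wilcoxon test properly serves the objective of a significant increase.

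Two more replies carry weight. The study protocol cited in section 14 (TD01-06-1C-06-02) was not supplied and may contain the rule. And no document requires a lower confidence limit above a threshold; that would be a stricter criterion on which statisticians can differ.

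**Conclusion.** The point holds within the supplied documents. Two figures, +15% and +200% (or +300%), are attached to what is evidently one study. Their relation is left to inference, and the wording of the larger one is ambiguous. The planned test cannot confirm either, and the SAP carries neither the protocol's own effect measure nor an interval for it.

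This conclusion rests on the text and on step 2 of the working. It does not depend on the assumed baseline means or SD ratios, which only illustrate. It should be fixed. Confidence is moderate, because the study protocol may already relate the two figures.

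**What to change.** **Protocol (section 7.1, Table 1, and the outcomes row in section 14).** State the role of each figure. Define the factor of three as a post/baseline ratio (3.0, if that is meant). Name the figure used for the Table 1 acceptance decision and the date it was set. If study protocol TD01-06-1C-06-02 holds the rule, cite it. If the date cannot be documented as before the results, report against both figures.

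**SAP.** Add the post/baseline ratio of mean appropriate recommendations. This equals the ratio of totals, since both counts come from the same cases, and (ratio − 1) × 100 gives the protocol's percentage increase. It also avoids per-patient percentages, which are undefined when a case has no appropriate recommendation at baseline. Give a 95% confidence interval that respects the pairing, for example a bootstrap over patients. Report estimate and interval against 1.15 and the defined threefold value, labelled post hoc if added after the data were seen. Keep the Wilcoxon test for the stated objective.

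Requiring the lower limit to exceed the threshold is optional. Without that rule, say only whether the point estimate meets the threshold and whether the interval excludes it.

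**Cost.** Some wording and one SAP paragraph, using counts already planned. A claim near a threshold may have to be worded less favourably. If the optional rule is adopted, simulations with n = 101, assumed baseline means of 3 to 12 and three assumed correlation models give a rough idea. A true ratio of 1.5 clears 1.15 in about 75–100% of runs, and a true 3.5 clears 3.0 in about 39–100%. A true ratio exactly at the threshold clears it in about 2–4%. These are illustrative only. The ratio of means with a bootstrap is one reasonable choice among several.

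### No planned analysis assesses the 15% benefit threshold, and the level at which the percentage formula applies is not stated

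*Protocol*

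**What the plan says.** **Threshold and formula.** In the protocol, section 14, Main clinical investigation (Primary and Secondary Outcomes), the stated clinical benefit is to "increase the number of appropriate recommendations by 15% over the recommendations generated with general management without the support system". The same row continues "To calculate the percentage increase between two values we will use the following formula" and gives the difference between post-intervention and baseline values, divided by the baseline value, times 100. The baseline is described thus: "The baseline/pre-test value is the number of appropriate recommendations based on clinical practice guidelines during conventional management (without CDSS"). It is not said to be a total, a mean or a patient's own count, and there is no rule for a baseline of zero.

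**A second threshold.** For the same outcome, Table 1 in section 11 requires: "Increase the number of appropriate recommendations by a factor of three". Section 7.1 says the same.

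**Analysis.** The SAP (Analysis of the amount and quality of recommendations) assesses the effect by "analyzing the *number* of recommendations (appropriate, inappropriate, missing) per patient". It then says: "The mean number of appropriate, inappropriate, and missing relevant recommendations generated per patient will be compared before and after the CDSS activation". For inference, "the Wilcoxon signed-rank test will be applied". Neither document gives an alpha, a margin or a confidence interval for the increase.

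**The concern.** The protocol sets a numerical benchmark for benefit and the SAP has no analysis that can say whether it was reached. A signed-rank test without a margin asks whether the before and after counts differ at all. A small increase can pass that test, so a significant p-value is silent on 15%. The percentage itself would be reported without any measure of its uncertainty.

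The formula can also be computed in more than one way: once from two totals or means, or once per patient and then averaged. These are different quantities. The second fails when a patient's baseline count is zero and gives most weight to patients with few baseline recommendations. If the choice is left open until the data are in hand, the reported percentage depends on it.

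**Working it through.** The plan contains no power or precision figure to reproduce.

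**Inputs.** From the documents: 101 cases, a 15% threshold, and each case assessed twice by the same panel. Not in the documents, so assumed: the baseline mean per case L, the distribution of the counts (Poisson, or Poisson with gamma variation between cases), the within-case correlation, and a two-sided alpha of 0.05.

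**1. Does a significant Wilcoxon result show 15%?** Simulated rejection rates with 101 cases:

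| True increase | Assumptions | Rejection rate |
|---|---|---|
| 5% | L 3 to 10, correlation 0 to 0.9 | 9% to 88% |
| 10% | same | 20% to 100% |
| 3% | system only adds recommendations, L 5 or 10 | over 99% |

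It does not: increases well below 15% can be significant.

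**2. Is the point estimate enough on the aggregate reading?** Let B = 101·L be the expected baseline total and P = r·B the expected post total, where r is the true ratio. The estimate exceeds 15% when post total − 1.15 × baseline total > 0. With independent Poisson counts that difference has mean P − 1.15B and variance P + 1.3225B. At a true increase of 10% (r = 1.10):

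| L | B | P | Mean | SD | z | Chance of exceeding 15% |
|---|---|---|---|---|---|---|
| 3 | 303 | 333.3 | −15.15 | 27.1 | 0.56 | 29% |
| 5 | 505 | 555.5 | −25.25 | 35.0 | 0.72 | 24% |
| 8 | 808 | 888.8 | −40.4 | 44.2 | 0.91 | 18% |

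Simulation agrees. If before and after counts share a common part, the variance falls by 2.3 × covariance. With covariance 0.8B the SDs at L = 3 and L = 8 are 13.3 and 21.7, z is 1.14 and 1.86, and the chance falls to 13% and 3%. At a true increase of exactly 15% the mean difference is zero, so about half of studies exceed the threshold whatever the correlation. With no effect (r = 1) and independent counts the chance is 4.3% at L = 3 and 1.3% at L = 5.

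**3. What if per-patient percentages were averaged?** With no effect and independent Poisson counts, dropping zero baselines, the expected average is L × E[1/X | X > 0] − 1, where X is the baseline count. At L = 3 this is 3 × 0.4327 − 1 = 30%; at L = 5, 5 × 0.2578 − 1 = 29%; at L = 8, 8 × 0.1469 − 1 = 17.5%; at L = 10, 13%. The expected number of zero-baseline cases is 101 × exp(−L): 5.0 at L = 3 and 0.7 at L = 5.

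Simulated chance that the study average exceeds 15% with no effect:

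| Model | Chance |
|---|---|
| Independent Poisson, L 3, 4, 5, 6, 8 | 89%, 93%, 90%, 83%, 61% |
| Independent Poisson, L 10, 15 | 36%, 6% |
| Independent Poisson, L 1 | 0.1% |
| Shared-part Poisson, correlation 0.5 | at most 53% |
| Shared-part Poisson, correlation 0.8 | at most 5% |
| Gamma variation between cases, L 2 to 10 | 24% to 87% |

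The source of the correlation matters. In the gamma model at L = 8 with correlation 0.80, the chance is still 59%, because the post count is redrawn around the case's own mean. If post counts simply repeat the baseline counts, it is 0%.

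**The case against.** The strongest reply is that the aggregate reading is the natural one. The formula speaks of two values and the SAP compares mean numbers, so two means go in and a ratio of means comes out. The hypertrophic cardiomyopathy study summarised in section 14 reports changes in that way: right answers from 1020 to 1032 and from 1074 to 1094, with percentages close to 12/1020 = 1.2% and 20/1074 = 1.9%. On that reading there is almost no bias, and zero baselines matter only if every case has one. This stands, although the worked example comes from another study.

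A reader might therefore infer too much from step 3, namely that the formula is usually above 15% when the system does nothing, so that success would be met by chance. The documents do not support that. Nowhere do they plan to average individual percentages, and they give neither the baseline mean nor the correlation on which the result depends. The 15% is worded as a relevance benchmark, not as the sole rule for success. The main objective asks for a significant increase, which the Wilcoxon test does address, and a chance average of 30% would be far from Table 1's factor of three.

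It can also be said that the outcome row belongs to a summary table which refers to a separate investigation plan, not supplied here, where the level may be defined. The SAP as supplied is still silent. None of these replies provides an interval or a test for the 15%.

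**Conclusion.** The point holds in this form: the 15% threshold has no planned analysis, and the level at which the formula applies is unstated. The first part follows from the documents alone. Its size depends on assumed counts. At a true increase of 10% a bare ratio of totals passes 15% in about 18% to 29% of studies (Poisson means 3 to 8, counts independent given the case), and less often if before and after counts largely overlap.

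The upward bias of averaged per-patient percentages is a conditional risk of leaving the level open. It is not a property of the plan as written. This should be corrected because it decides what the study can say about its own benchmark; it does not undermine the comparison against no difference.

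**What to change.** Add one paragraph to the SAP:

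- Define the percentage increase as (sum of post counts / sum of baseline counts − 1) × 100 over all cases.
- Report it with a 95% confidence interval from a bootstrap that resamples cases, so that each case's before and after counts stay together.
- Base any statement that the threshold is met on that interval, not on the point estimate or the Wilcoxon p-value. State in advance how the interval will be read. Requiring the lower limit to exceed the threshold is the strict option, but not the only defensible one.
- Keep the Wilcoxon test for the objective of a significant increase.
- Reconcile the 15% in section 14 with the factor of three in sections 7.1 and 11, so that the interval is compared with one stated threshold. If the factor of three means post = 3 × baseline, it is +200% on the formula's scale.

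The per-patient counts already planned are enough, so no new data are needed. The cost is that the threshold becomes harder to claim than with a point estimate. Section 14 lists the study among investigations undertaken, dated 2024. If the data have already been seen, the analysis should be labelled as added afterwards.
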